### 12.1.4 Adverse Device Effect

Any AE related to the use of an investigational device is adverse device effect (ADE).

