### **3.1.3 V.A.C. VERAFLTM Dressing Kit**

Since the introduction of NPWT, a variety of new therapies and dressings have been developed in order to better meet the needs of patients with wounds. In 1998, Fleischmann et al described the coupling of NPWT with timed, intermittent, gravity fed delivery of a topical solution. KCI® later developed and commercialized this technology as the V.A.C Instill® Wound Therapy System in 2003. The latest development in V.A.C® technology is the V.A.C. UTLATM Therapy System which integrates both V.A.C® Therapy and instillation into one therapy unit. The V.A.C. UTLATM Therapy System consists of a new programmable therapy pump and a specialized dressing system (V.A.C. VERAFLTM Dressing Kit).

V.A.C. VERAFLTM Dressing Kit, which is the investigational device, is a reticulated

open-cell foam polyurethane ester dressing that is designed to be hydrophobic to deliver the various compatible topical wound instillation solution(s) to the wound site for therapy. The V.A.C. VERALFOTM Dressing Kit is a 510(k) -cleared, Class II device (K100657), which was approval in July 2010 by FDA. V.A.C. VERAFLDTM Dressing Kit with V.A.C. ULTA™ Therapy System is intended to create an environment that promotes wound healing by secondary or tertiary (delayed primary) intention by preparing the wound bed for closure, reducing edema, promoting granulation tissue formation and perfusion, and by removing exudates and infectious material. The instillation option is indicated for patients who would benefit from vacuum assisted drainage and controlled delivery of topical wound treatment solutions and suspensions over the wound bed.

In at least two clinical studies, enhanced granulation tissue formation has been observed using V.A.C. VERAFLDTM Dressing with saline instillation. This has been corroborated in one porcine study.

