### 5.3.2 Evaluation of Safety

#### (1) Incidence of AEs (unit: %)

**Define:** an AE is any untoward medical occurrence in the course of a trial, whether or not related to the investigational device.

**Evaluation:** type, incidence, seriousness and relatedness of AEs/Adverse device effects (ADEs), and laboratory abnormalities will be reported.

**Formula:** incidence of AEs/ADEs = sum of subject who occurred AEs/ADs ÷ sum of subjects for each group × 100%.

**Statistical method:** the difference between investigational group and control group will be assessed.

**Note:** especially focus on the systemic reactions and local skin/tissue irritation (such conditions as wound secretions and swelling, pain, and local skin color change, etc.)

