#### (2) Incidence of SAEs (unit: %)

**Define:** see relevant subsections of Section 12.2.1.

**Evaluation:** incidence, and relatedness of SAEs/Serious adverse device effects (SADEs) will be reported.

**Formula:** incidence of SAEs/SADEs = sum of subject who occurred SAEs/SADEs ÷ sum of subjects for each group × 100%.

**Statistical method:** The difference between investigational group the control group will be assessed.

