### **12.2.2 Serious Adverse Device Effect**

A serious adverse device effect (SADE) is an ADE that has resulted in any of the consequences characteristic of serious adverse event.

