### **12.3 Device Deficiency**

#### **12.3.1 Definition**

Device deficiency refer to any irrational risk in trial, such as tag errors, quality issues, failure, which may threaten subjects' health and safety while investigational device is under normal use.

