#### **12.3.2 Recording and Reporting for the Device Deficiency**

Investigators should record device deficiency in trial and analyze event cause with the sponsor.

At any stage of trial, both investigators and subjects can lodge complaints on the investigational device or the control device.

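### ADE, SADE and device deficiency are defined by the investigational device yet compared between arms: control-arm ADEs may or may not count, and control-arm deficiencies do not count as written

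*Protocol*

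**What the plan says.** **Definitions.** Protocol 12.1.4 reads "Any AE related to the use of an investigational device is adverse device effect (ADE", and SAP 18.1.5 repeats the sentence. Protocol 12.2.2 builds on it: "A serious adverse device effect (SADE) is an ADE that has resulted in any of the consequences characteristic of serious adverse event". Protocol 12.3.1 describes a device deficiency as a risk to subjects' "health and safety while investigational device is under normal use".

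**Which device is meant.** Protocol 3.1.3 identifies it: "Dressing Kit, which is the investigational device, is a reticulated" open-cell foam dressing. The control device is named as something else. In Protocol 12.3.2, for example, "both investigators and subjects can lodge complaints on the investigational device or the control device".

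**How the definitions are used.** Protocol 5.3.2 (1) gives the formula "incidence of AEs/ADEs = sum of subject who occurred AEs/ADs ÷ sum of subjects for each group × 100"% and says that "the difference between investigational group and control group will be assessed". Items (2), on SAEs and SADEs, and (3), on device deficiencies, also use per-group formulas and say: "The difference between investigational group the control group will be assessed". Device deficiencies are named in the secondary objectives (Protocol 4.2, SAP 3.2); ADEs and SADEs are not.

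**Competing wording.** The causality scale in Protocol 12.1.3 is framed around the *study intervention*. SAP 18.1.5, after repeating the ADE definition, classes an AE as related when its relationship to the *study device* is definite, probable or possible. It treats a missing rating as probable.

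**Testing.** SAP 17.1–17.3 plan chi-square or Fisher's exact tests. SAP section 18 says that safety variables will not be compared statistically.

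**The concern.** A comparison between arms needs an endpoint that can occur in both. Read literally, an event caused by the control dressing is neither an ADE nor a SADE, and a fault in the control dressing is not a device deficiency. The control arm would then show zero however that dressing performed, and the comparison could only go against the investigational device.

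The practical risk is wider than that. Investigators are not blinded (Protocol 5.1.2.4), so each knows which device is in place when rating causality. One site may rate control-arm events against the control dressing; another may follow Protocol 12.1.4 and rate none of them as device effects. The control rate would then partly reflect how sites read a definition. Ratings made on different bases cannot be put right later by SAP wording.

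This is a registration trial, and a reader of the report will compare device-attributed harm between the two arms whether or not a p-value is shown.

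**Working it through.** The plan states no ADE, SADE or deficiency rate, so there is no figure to reproduce. The check has two parts.

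**1. Can a control-arm event be counted?**

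| Endpoint | Text that excludes the control device | Text that can include it | Result |
|---|---|---|---|
| ADE | Protocol 12.1.4; first definition in SAP 18.1.5 | Protocol 12.1.3 (*study intervention*); classification rule in SAP 18.1.5 (*study device*) | Contradictory |
| SADE | Protocol 12.2.2, through the ADE definition | As for ADE | Contradictory |
| Device deficiency | Protocol 12.3.1 | None in the definition; Protocol 12.3.2 only accepts complaints | Zero in the control arm as written |

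*Study device* does reach both arms: SAP 7.1 and 7.2 use its first application to set the reference date and baseline for every subject. But SAP 18.1.5 puts the narrow definition and the broader rule side by side and does not say which governs. For deficiencies, SAP 17.3 refers back to the protocol definition and so adds nothing.

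The negative-pressure source is also unplaced. Protocol 5.4.1 lists the therapy unit separately from the investigational device, and 5.4.2 gives wall suction for the control. The anticipated events in Protocol 12.1.5 nevertheless include burns from the therapy unit and wrong unit settings.

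**2. What would a control count fixed at zero do?** (illustration)

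Inputs: 70 and 85 subjects per arm (Protocol 6.1.1); two-sided 5% level (SAP 7.5); Fisher's exact test, one of the two tests named in SAP 17.1–17.3; equal true rates of 5%, 10% or 15% in both arms, which are assumed.

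With *x* investigational subjects against 0 and *n* per arm, the two-sided p-value is 2 × C(*n*, *x*) / C(2*n*, *x*).

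- *n* = 70: *x* = 5 gives 0.058; *x* = 6 gives 0.028.
- *n* = 85: *x* = 5 gives 0.059; *x* = 6 gives 0.029.

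The threshold is therefore 6 subjects at either size. The chance of reaching it when the devices are truly alike is P(X ≥ 6) for X ~ Binomial(*n*, rate):

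| Assumed true rate in both arms | 70 per arm | 85 per arm |
|---|---|---|
| 5% | 14% | 25% |
| 10% | 71% | 86% |
| 15% | 96% | 99% |

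If control events are counted on the same basis, 6 against 6 gives p = 1.0.

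**The case against.** A reader might infer that the control arm's ADE and SADE incidence is zero by definition. The documents do not support that. The rule closest to the tables, in SAP 18.1.5, works from the study device, which every subject receives. The missing-rating rule has no limit by arm, and SAP 18.1.1 tabulates ADEs and SADEs by treatment group. On that text control-arm events can be counted.

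The narrow term also looks like loose drafting. The AE definition in Protocol 12.1.1 mentions only the investigational device, yet plainly covers both arms. The Schedule of Activities collects device deficiencies with no distinction by arm.

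Nor is a test on ADEs or SADEs clearly planned. In SAP 17.1 and 17.2 those terms appear in the formulas, but the statistical-method sentences name only AEs and SAEs. SAP 18.1.5 and 18.1.6 provide listings and summaries, and section 18 rules out comparison.

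All of this stands against the zero-by-definition reading for ADE and SADE, and against treating the percentages as a property of the plan. It does not settle which wording sites and programmers should follow. It also does not help device deficiency: the likely intention is to count both arms, but no definition says so, and SAP 17.3 does plan a test with p-values, for deficiencies that lead to an AE or SAE.

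**Conclusion.** The point holds as an inconsistency in definitions. For ADE and SADE the documents contradict themselves, so the control rate depends on which wording is applied. For device deficiency there is no competing definition, and applied as written the control rate is zero.

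The size is conditional. A threshold of 6 against 0, and a false-signal chance of 14% to 96% at 70 per arm or 25% to 99% at 85, requires four things together: the literal reading at every site, a Fisher test actually run, equal true rates, and rates between 5% and 15% that appear nowhere in the documents.

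A reader might also take this to be the trial's main safety comparison. It is not: the secondary objectives name AEs, SAEs and device deficiencies. Overall AE and SAE incidence does not depend on the ADE definition, and the primary non-inferiority conclusion is untouched. The literal reading biases against the investigational device, so it would not create a false safety claim in its favour.

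**What to change.** - In Protocol 12.1.4, 12.2.2 and 12.3.1 and SAP 17.3 and 18.1.5, define ADE, SADE and device deficiency, for between-group analysis, as relating to the assigned study device in either arm, including its negative-pressure source.
- Use that one term in the causality scale of Protocol 12.1.3 and tell sites to rate both arms on that basis.
- Keep the investigational-only scope for expedited regulatory reporting (Protocol 12.1.6 and 12.2.3), and say that it serves that purpose only.
- Reconcile SAP 17.1–17.3 with section 18: state whether ADE, SADE and deficiency incidences are tested or only described.

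The cost is a few sentences in each document and a completion note for sites. SAP 18.1.5 indicates that investigators already record a relationship rating, so a new data field is probably not needed. The case report form is not among the documents, so this should be checked, together with the basis on which any control-arm ratings already made were given.

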### 12.1.5 Anticipated AE

Anticipated AEs with NPWT Therapy/Dressing for this trial are summarized in following table.

Skin and Subcutaneous Tissue Reaction/Allergy	Desiccation/injury Skin rash, irritation, blistering Pruritus/itching Skin excoriation/breakdown Skin stripping Skin scarring if significant skin irritation were to occur Maceration Skin hyper/hypo-pigmentation at and/or around dressing application area Erythema/redness, edema, inflammation, or swelling at and/or around dressing application area
Mild Pain or Discomfort	Tenderness/minor ache at and/or around dressing application area Perspiration associated with wearing dressing Auditory irritation (due to mild buzzing sound of negative pressure unit) Decreased sleep or sleep quality Paresthesia (numbness, tingling, prickling, creeping sensation)
Other	Bleeding Cardiac compromise (vagal response, bradycardia) Pulmonary compromise Accidental instillation in a body cavity Localized infection Autonomic dysreflexia (in subjects with spinal cord injury) Retained foreign debris (e.g. foam) in the wound Impairment of mobility/activity (limitation secondary to weight and attachment of therapy unit) Possible tubing entanglement/trip or slip hazard leading to fracture, tissue damage Incorrect therapy unit settings resulting in incorrect frequency/dosing Tunneling Stalled healing/non-progression of healing Deterioration of the wound Systemic reaction (due to allergic reaction to dressing materials)

	Burn secondary to therapy unit or power cord malfunction
--	--

### **12.1.6 Adverse Event Reporting**

Investigators shall record AE identified during clinical trials of medical devices. Investigators deal with AEs with target treatment and follow-up, until symptoms disappear or become stable or otherwise a reasonable explanation.

The investigators shall provide adequate and timely therapy and treatment for the subjects in case of any AE in medical device clinical trial and inform the subjects in time when they need therapy and treatment for complicated diseases.

Within 24 hours after learning about the SAE, investigators shall report to the sponsor, the management department and the EC of the medical devices clinical trial institution . At the same time, investigators shall also follow up the SAE according to the clinical trial protocol and submit a follow-up report of SAE.

Within 7 days after learning that death or life-threatening SAEs related to investigational medical device under clinical trial, and within 15 days after learning that non-death or non-life-threatening SAEs related to investigational medical device under clinical trial or other serious safety risks, the sponsor shall report to other medical device clinical trial institutions, the EC and principal investigators involved in the clinical trial, to the drug regulatory departments in the province, autonomous region or municipality directly under the Central Government where the sponsor is located, and to the drug regulatory departments and health administration departments in the provinces, autonomous regions or municipalities directly under the Central Government where the medical device clinical trial institutions are located and take risk control measures.

In case of any information that may affect the safety of subjects and the implementation of medical device clinical trials, or change the approval opinions of the EC, the sponsor shall promptly organize the modification of the clinical trial protocol, the ICF and other information provided to the subjects as well as other relevant documents, and submit them to the EC for review.

In case of any SAE on the medical device under clinical trial on a large scale or any other major safety problems, the sponsor shall suspend or terminate clinical trials of medical devices and report to the management department of all medical devices clinical trial institutions, the EC and principal investigators, to the drug regulatory departments in the province, autonomous region and municipality directly under the Central Government where the sponsor is located, and to the drug regulatory departments and health administration departments in the provinces, autonomous regions and municipalities directly under the Central Government where all clinical trial institutions of medical devices are located.

## **12.2 Serious Adverse Event**

### **12.2.1 Definition**

An AE that

- (1) led to death or
- (2) serious deterioration in the health of the subject during medical device clinical trials, including:
  - fatal disease or damage; or
  - perpetual defects of physical structure or physical function; or
  - requires patients' hospitalization or prolonging of hospital stay; or
  - requires medical measures to avoid perpetual defects of physical structure or physical function;
- (3) fetal distress, fetal death or congenital abnormality and congenital defects.
- (4) Other medically significant event.

**Note:** Planned hospitalization for a pre-existing condition or a procedure required by the clinical investigation plan, without serious deterioration in health is not considered a SAE.

### **12.2.2 Serious Adverse Device Effect**

A serious adverse device effect (SADE) is an ADE that has resulted in any of the consequences characteristic of serious adverse event.

### **12.2.3 Reports of SAEs**

When SAE occur in clinical trials of medical devices, investigators shall immediately take appropriate treatment measures for the subjects. Within 24 hours after learning about the SAE, investigators shall report to the sponsor, the management department and the EC of the medical devices clinical trial institution. At the same time, investigators shall also follow up the SAE according to the clinical trial protocol and submit a follow-up report of SAE.

Sponsor shall evaluate and report the safety information during clinical trials of medical devices.

Within 7 days after learning that death or life-threatening serious SAEs related to investigational medical device under clinical trial, and within 15 days after learning that non-death or non-life-threatening SAEs related to investigational medical device under clinical trial or other serious safety risks, the sponsor shall report to other medical device clinical trial institutions, the EC and principal investigators involved in the clinical trial, to the drug regulatory departments in the province, autonomous region or municipality directly under the Central Government where the sponsor is located, and to the drug regulatory departments and health administration departments in the provinces, autonomous regions or municipalities directly under the Central Government where the medical device clinical trial institutions are located and take risk control measures.

In case of any information that may affect the safety of subjects and the implementation of medical device clinical trials, or change the approval opinions of the EC, the sponsor shall promptly organize the modification of the clinical trial protocol, the ICF and other information provided to the subjects as well as other relevant documents, and submit them to the EC for review.

In case of any SAE on the medical device under clinical trial on a large scale or any other major safety problems, the sponsor shall suspend or terminate clinical trials of medical devices and report to the management department of all medical devices

clinical trial institutions, the EC and principal investigators, to the drug regulatory departments in the province, autonomous region and municipality directly under the Central Government where the sponsor is located, and to the drug regulatory departments and health administration departments in the provinces, autonomous regions and municipalities directly under the Central Government where all clinical trial institutions of medical devices are located.

### **12.3 Device Deficiency**

#### **12.3.1 Definition**

Device deficiency refer to any irrational risk in trial, such as tag errors, quality issues, failure, which may threaten subjects' health and safety while investigational device is under normal use.

#### **12.3.2 Recording and Reporting for the Device Deficiency**

Investigators should record device deficiency in trial and analyze event cause with the sponsor.

At any stage of trial, both investigators and subjects can lodge complaints on the investigational device or the control device.

### **12.4 Reporting Procedure and Contact Information**

When SAE occur in clinical trials of medical devices, investigators shall immediately take appropriate treatment measures for the subjects. Within 24 hours after learning about the SAE, investigators shall report to the sponsor, the management department and the EC of the medical devices clinical trial institution. At the same time, they shall also follow up the SAE according to the clinical trial protocol and submit a follow-up report of SAE. In this study, CRO Corporation Kun Tuo will report on SAEs on behalf of the sponsor. Report contact: Kun Tuo's clinical safety management department, e-mail: [[contact]](mailto:[contact]).

## **13 Deviations and Amendments to the Protocol**

### **13.1 Deviations**

Any act of intentional or unintentional variation of the protocol is defined as protocol

deviation (PD).

### **13.2 Amendments to the Protocol**

After ECs approve the protocol, if there is any modification, "declaration for protocol revision" is required, which should be signed by principal investigators and approved by EC before implementation.

After amendments, revised protocol shall be approved and signed by sponsor firstly.

### **14 Direct Access to Source Data and Documents**

The definition of source data and source documents in *GCP (2022)* is as follows:

Source data refers to the source records of clinical findings, observations and other activities in medical device clinical trials, as well as all information in approved copies, which can be used for medical device clinical trial reconstruction and evaluation.

Source Documents include printed files, visual files, or electronic files which contain source data.

In this trial, the principal investigators and authorized investigators can access, yield and modify inpatient records, ICF, eCRF, any source medical records in Hospital Information Systems (HISs) which support information management and on-line operation in hospital management and medical activities. Laboratory testers and investigators can access and yield testing reports.

Data management personnel can access and yield data-management data; Statistical analysts can access and yield statistical analysis data.

Limits of Authority to access and edit other source data shall be specified by the standard operating procedure (SOP) of the corresponding departments, in accordance with relevant laws, regulations and technical standards in China.

### **15 Contents of Clinical Study Report**

According to *GCP (2022)*, contents of clinical study report should at least include the basic information, implementation, statistical analysis methods, clinical trial results, reports and treatment of AEs and device defect, analysis and discussion of clinical trial results, clinical trial conclusions, ethical description, existing problems and

improvement suggestions of medical devices clinical trial.

